All pediatric patients in the age group of 5 to 10 years presenting with acute abdomen diagnosed clinically and radiologically to be having a diagnosis of secondary peritonitis and obstruction; who were adequately resuscitated (with a minimum resuscitation period of at least 1 hour) pre-operatively and underwent definitive surgery by a single surgeon (pediatric surgery senior resident) in the emergency were included in the study. Also, only those patients who had a PRISM-III (Pediatric Risk of Mortality III) score (Figure 1) of ≤ 8 at presentation were included to avoid the confounding effect of pre-operative variables that might affect mortality. All patients were adequately resuscitated in terms of temperature, central nervous system (Glasgow Coma Scale, pupillary reflexes), cardiovascular system (systolic blood pressure, heart rate) and respiratory system (oxygen saturation $> 95\%$, $p\text{CO}_2$, pH, PaO_2) parameters so that they were brought within 0 score range of PRISM-III score at the end of resuscitation and before shifting to the operation theatre. Furthermore for inclusion only those pediatric patients were considered who presented within 72 hours of initial onset of symptoms, operated within 24 hours of initial presentation and who died in index hospital admission within 30 days.

Patients who underwent damage control surgery, whose PRISM – III score was >9 at any point of time before undergoing laparotomy or inability to achieve adequate resuscitation (PRISM-III score >0 before shifting to operation theatre) and/or requirement of resuscitation beyond 4 hours of presentation were excluded from the study.

All the patients were shifted to pediatric intensive care unit (PICU) after the operation where dedicated staff and pediatrician were available for monitoring of patient.

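### Do the two PRISM-III limits, ≤ 8 to enter and > 9 to exclude, leave eligibility ill-defined at a score of 9?

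*Protocol*

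**What the plan says.** Both limits are in the eligibility text of the protocol's Materials & Methods section.

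- **Inclusion.** The restriction begins "only those patients who had a PRISM-III" and continues with a "score (Figure 1) of ≤ 8 at presentation were included". The stated purpose is "to avoid the confounding effect of pre-operative variables that might affect mortality". This is the only reason given for either limit.
- **Exclusion, next paragraph.** A child is removed if the "score was >9 at any point of time before undergoing laparotomy". That window starts at or before presentation, so it overlaps the moment at which the inclusion limit applies.
- **Two further exclusions in the same sentence.** One is failure of resuscitation, defined as "PRISM-III score >0 before shifting to operation theatre". The other is "requirement of resuscitation beyond 4 hours of presentation were excluded from the study".

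The text does not say whether the step from 8 to 9 is intended.

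**The concern.** An exclusion limit is often written as the mirror image of the inclusion limit. Here it is not: the mirror of ≤ 8 would be > 8, and the protocol has > 9. A reader may suspect that one figure is a typing error, or that a score of 9 has been left without a rule.

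The stake would be confounding. The primary objectives are to quantify the effect of laparotomy duration on mortality and to find a rough cut-off. The PRISM-III entry limit is the restriction that the protocol expressly ties to confounding by pre-operative state. If children who had been sicker before surgery got through a loose limit, and if they also had systematically longer or shorter operations, the association between duration and mortality could be distorted. A vague boundary would also stop another group from reproducing the study population.

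**Working it through.** **Inputs.** From Materials & Methods: entry limit ≤ 8 at presentation; exclusion if > 9 at any pre-operative time; score 0 required before theatre; resuscitation not beyond 4 hours of presentation. Assumption: scores are whole numbers (the score table, Figure 1, is not shown). The plan states no sample size, power or error rate that bears on this point, so there is no figure of its own to reproduce.

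**Step 1: apply both rules together.** Take children who meet the score-0 and 4-hour rules, and classify them by score at presentation and highest pre-operative score.

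| Score at presentation | Highest pre-operative score | Inclusion rule (≤ 8) | Exclusion rule (> 9) | Result |
|---|---|---|---|---|
| 0 to 8 | up to 8 | met | not triggered | in |
| 0 to 8 | 9 | met | not triggered | in |
| 0 to 8 | 10 or more | met | triggered | out |
| 9 | 9 | not met | not triggered | out |
| 9 | 10 or more | not met | triggered | out |
| 10 or more | 10 or more | not met | triggered | out |

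Every row has exactly one result. The score of 9 is the only value whose handling depends on when it occurs: out at presentation, allowed as a later peak. No child is both admitted and excluded, and none is left unclassified. If fractional scores were possible, the affected range would be above 8 up to and including 9, and classification would still be unique.

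**Step 2: how narrow the path is.** To be affected, a child must arrive at 0 to 8, peak at exactly 9, return to 0 before theatre and not need resuscitation beyond 4 hours. The protocol gives no sample size, number of deaths or score distribution, so the count cannot be derived.

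**Step 3: can a bias be sized?** For a comparison of long with short operations, the mortality risk ratio would be multiplied by

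[1 + f1(r − 1)] / [1 + f0(r − 1)],

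where f1 and f0 are the fractions of children who peaked at 9 among long and short operations, and r is their mortality risk relative to the other children. None of these values is in the protocol. Assumed values show the range:

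- f1 = 1%, f0 = 0, r = 1.5: 1 + 0.01 × 0.5 = 1.005
- f1 = 5%, f0 = 0, r = 3: 1 + 0.05 × 2 = 1.10
- f1 = 0, f0 = 5%, r = 3: 1 / 1.10 = 0.91
- f1 = f0: 1.00 for any r

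The sign depends wholly on whether children who peaked at 9 had long or short operations, and the protocol says nothing about that. These figures illustrate the formula and are not evidence of bias.

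**The case for a change.** The strongest case for acting is this. The only reason given for either limit is the avoidance of confounding, and it does not explain why a child who worsens to 9 is acceptable when a child who arrives at 9 is not. The score-0 rule narrows the path without closing it. The plan's writers evidently thought the peak score mattered, since they wrote a separate rule for it. Eligibility belongs in the protocol, so a separate SAP would not be expected to settle the point. A clarifying sentence would cost almost nothing.

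Much of this stands. The difference is real, it is unexplained, and a sentence saying whether two limits are meant would be tidier. Two things do not follow, however. First, an unexplained difference is not an ambiguous rule: two people applying the text literally would classify every child alike, so reproducibility is not lost. A stricter limit at entry and a slightly looser one over a longer window can coexist. Second, going further, to a count of children who peaked at 9 and a repeat mortality analysis without them, would need peak scores. The protocol does not say how often the score was recorded between presentation and theatre, so it is unknown whether such peaks can be recovered, and the analysis might concern no child at all.

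**Conclusion.** The observation is correct on the text, but it calls for no change to the plan. The two limits differ at one score value, apply to different time windows, and together define the study population uniquely. Using them as written gives no demonstrably wrong result. The requirement closest to surgery, a score of 0 before theatre, applies to every child whatever the earlier peak.

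The size is unknown and probably small. Under the assumed inputs above the mortality risk ratio could move by a factor between 0.91 and 1.10, with 1.00 if a peak of 9 is unrelated to operative duration. The document supports no particular value or direction. The conclusion rests on whole-number scoring for the statement that 9 alone is affected, and on a literal reading of both rules. Whether the one-point step was deliberate or clerical cannot be told from the protocol, and which limit is preferable is not judged here. A report of the study can state both limits as they stand.
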